Appendix 3 Clinical Laboratory Tests

- The tests detailed in [Table 10](#) will be performed by the local laboratory.
- Protocol-specific requirements for inclusion or exclusion of subjects are detailed in Section [5.0](#) of the protocol.
- Additional tests may be performed at any time during the study as determined necessary by the investigator or required by local regulations.

Table 10 Protocol-required Safety Laboratory Assessments

Laboratory Assessments	Parameters											
Haematology	Platelet count		RBC Indices: Mean corpuscular volume (MCV) Mean corpuscular haemoglobin (MCH)	White blood cell count with differential: Neutrophils Lymphocytes Monocytes Eosinophils Basophils								
	Red blood cell (RBC) count											
	Haemoglobin											
	Haematocrit											
Clinical chemistry ^a	Blood urea nitrogen	Potassium	Aspartate aminotransferase (AST)/ Serum glutamic-oxaloacetic transaminase (SGOT)	Total and direct bilirubin								
	Creatinine	Sodium	Alanine aminotransferase (ALT)/ Serum glutamic-pyruvic transaminase (SGPT)	Total protein								
	Glucose (nonfasting)	Calcium	Alkaline phosphatase GGT (gamma glutamyl transferase)									
Urine and serum pregnancy test (HCG)	
 At screening, within 72 hours prior to treatment, then every 6 weeks and at EOS 											
Thyroid function test (blood)	
 At Visits 1a, 3, 5, 7 (Weeks 1, 7, 13, and 19) and each 6 weeks intervals 											
C-reactive protein (CRP)	
 At screening and at each visit during the treatment period and at EOS 											
NOTES: Hematology, chemistry and CRP will be done at each visit during the treatment period and at EOS visit. In addition, if it is scheduled to administer BO-112, a coagulation test will also be done.												
^a Details of liver chemistry stopping criteria and required actions and follow-up assessments after liver stopping or monitoring event are given in Section 7.1 . All events of ALT $\geq 3 \times$ upper limit of normal (ULN) and bilirubin $\geq 2 \times$ ULN ($>35\%$ direct bilirubin) or ALT $\geq 3 \times$ ULN and international normalised ratio (INR) >1.5 , if INR measured, which may indicate severe liver injury (possible Hy's Law), must be reported as an SAE (excluding studies of hepatic impairment or cirrhosis).												

Investigators must document their review of each laboratory safety report.

Appendix 4 Adverse Events: Definitions and Procedures for Recording, Evaluating, Follow-up, and Reporting

Definition of AE

AE Definition

 • An AE is any untoward medical occurrence in a patient or subject, temporally associated with the use of study treatment, whether or not considered related to the study treatment. • NOTE: An AE can therefore be any unfavourable and unintended sign (including an abnormal laboratory finding), symptom, or disease (new or exacerbated) temporally associated with the use of study treatment.

Events Meeting the AE Definition

 • Any abnormal laboratory test results (haematology, clinical chemistry, or urinalysis) or other safety assessments (eg, ECG, radiological scans, and vital signs measurements), including those that worsen from baseline, considered clinically significant in the medical and scientific judgement of the investigator (ie, not related to progression of underlying disease). • Exacerbation of a chronic or intermittent pre-existing condition including either an increase in frequency and/or intensity of the condition. • New conditions detected or diagnosed after study treatment administration even though it may have been present before the start of the study. • Signs, symptoms, or the clinical sequelae of a suspected drug-drug interaction. • Signs, symptoms, or the clinical sequelae of a suspected overdose of either study treatment or a concomitant medication. Overdose per se will not be reported as an AE/SAE unless it is an intentional overdose taken with possible suicidal/self-harming intent. Such overdoses should be reported regardless of sequelae. • "Lack of efficacy" or "failure of expected pharmacological action" per se will not be reported as an AE or SAE. Such instances will be captured in the efficacy assessments. However, the signs, symptoms, and/or clinical sequelae resulting from lack of efficacy will be reported as AE or SAE if they fulfil the definition of an AE or SAE.

Events NOT Meeting the AE Definition

 • Any clinically significant abnormal laboratory findings or other abnormal safety assessments which are associated with the underlying disease, unless judged by the investigator to be more severe than expected for the subject's condition. • The disease/disorder being studied or expected progression, signs, or symptoms of the disease/disorder being studied, unless more severe than expected for the subject's condition. • Medical or surgical procedure (eg, endoscopy, appendectomy): the condition that leads to the procedure is the AE. • Situations in which an untoward medical occurrence did not occur (social and/or convenience admission to a hospital). • Anticipated day-to-day fluctuations of pre-existing disease(s) or condition(s) present or detected at the start of the study that do not worsen.

Definition of SAE

If an event is not an AE per definition above, then it cannot be an SAE even if serious conditions are met (eg, hospitalisation for signs/symptoms of the disease under study, death due to progression of disease).

An SAE is defined as any untoward medical occurrence that, at any dose:	
a) Results in death	
b) Is life-threatening	
The term ‘life-threatening’ in the definition of “serious” refers to an event in which the subject was at risk of death at the time of the event. It does not refer to an event, which hypothetically might have caused death, if it were more severe.

c) Requires inpatient hospitalisation or prolongation of existing hospitalisation	
In general, hospitalisation signifies that the subject has been detained (usually involving at least an overnight stay) at the hospital or emergency ward for observation and/or treatment that would not have been appropriate in the physician’s office or outpatient setting. Complications that occur during hospitalisation are AEs. If a complication prolongs hospitalisation or fulfils any other serious criteria, the event is serious. When in doubt as to whether “hospitalisation” occurred or was necessary, the AE should be considered serious.
 
Hospitalisation for elective treatment of a pre-existing condition that did not worsen from baseline is not considered an AE.

d) Results in persistent disability/incapacity	
 The term disability means a substantial disruption of a person’s ability to conduct normal life functions. This definition is not intended to include experiences of relatively minor medical significance such as uncomplicated headache, nausea, vomiting, diarrhoea, influenza, and accidental trauma (eg, sprained ankle) which may interfere with or prevent everyday life functions but do not constitute a substantial disruption.
e) Is a congenital anomaly/birth defect	
f) Other situations:	
 Medical or scientific judgement should be exercised in deciding whether SAE reporting is appropriate in other situations such as important medical events that may not be immediately life-threatening or result in death or hospitalisation but may jeopardise the subject or may require medical or surgical intervention to prevent 1 of the other outcomes listed in the above definition. These events should usually be considered serious. 
Examples of such events include invasive or malignant cancers, intensive treatment in an emergency room or at home for allergic bronchospasm, blood dyscrasias, or convulsions that do not result in hospitalisation, or development of drug dependency or drug abuse.

Recording and Follow-up of AE and/or SAE

AE and SAE Recording

 When an AE/SAE occurs, it is the responsibility of the investigator to review all documentation (eg, hospital progress notes, laboratory reports, and diagnostics reports) related to the event. The investigator will then record all relevant AE/SAE information in the eCRF. Each event must be recorded separately. It is not acceptable for the investigator to send photocopies of the subject's medical records to Highlight Therapeutics in lieu of completion of the BOT112-02/AE/SAE eCRF page. There may be instances when copies of medical records for certain cases are requested by Highlight Therapeutics. In this case, all subject identifiers, with the exception of the subject number, will be redacted on the copies of the medical records before submission to Highlight Therapeutics. The investigator will attempt to establish a diagnosis of the event based on signs, symptoms, and/or other clinical information. Whenever possible, the diagnosis (not the individual signs/symptoms) will be documented as the AE/SAE.
Assessment of Intensity

The investigator will make an assessment of intensity for each AE and SAE reported during the study and assign it to 1 of the following categories:
 
 Mild: An event that is easily tolerated by the subject, causing minimal discomfort and not interfering with everyday activities. Moderate: An event that causes sufficient discomfort and interferes with normal everyday activities. Severe: An event that prevents normal everyday activities. An AE that is assessed as severe should not be confused with an SAE. Severe is a category utilised for rating the intensity of an event; and both AEs and SAEs can be assessed as severe. 
An event is defined as 'serious' when it meets at least 1 of the predefined outcomes as described in the definition of an SAE, NOT when it is rated as severe.
 
 National Cancer Institute-Common Terminology Criteria for Adverse Events (NCI-CTCAE) v5.0 will be used for severity grading.

Assessment of Causality

 The investigator is obligated to assess the relationship between study treatment and each occurrence of each AE/SAE. The AE must be characterised as unrelated, unlikely to be related, possibly related, probably related, or unknown (unable to judge). 
 “Probably related” conveys that there are facts, evidence, and/or arguments to suggest a causal relationship, rather than a relationship cannot be ruled out. “Possibly related” suggests that the association of the AE with the study treatment is unknown; however, the AE is not reasonably supported by other conditions. “Unlikely to be related” suggests that only a remote connection exists between the study treatment and the AE. Other conditions, including chronic illness, progression or expression of the disease-state or reaction to concomitant therapy, appear to explain the reported AE. “Unrelated” is used if there is not a reasonable possibility that the study treatment caused the AE. All efforts should be made to classify the AE according to the above categories. The category “unknown” (unable to judge) may be used only if the causality is not assessable, eg, because of insufficient evidence, conflicting evidence, conflicting data, or poor documentation. The investigator will use clinical judgement to determine the relationship.

- Alternative causes, such as underlying disease(s), concomitant therapy, and other risk factors, as well as the temporal relationship of the event to study treatment administration will be considered and investigated.
- The investigator will also consult the Investigator's Brochure and/or Product Information, for marketed products, in his/her assessment.
- For each AE/SAE, the investigator must document in the medical notes that he/she has reviewed the AE/SAE and has provided an assessment of causality.
- There may be situations in which an SAE has occurred, and the investigator has minimal information to include in the initial report to appropriate regulatory authorities. However, it is very important that the investigator always make an assessment of causality for every event before the initial transmission of the SAE data to appropriate regulatory authorities.
- The investigator may change his/her opinion of causality in light of follow-up information and send an SAE follow-up report with the updated causality assessment.
- The causality assessment is one of the criteria used when determining regulatory reporting requirements.

Follow-up of AEs and SAEs

- The investigator is obligated to perform or arrange for the conduct of supplemental measurements and/or evaluations as medically indicated or as requested by Highlight Therapeutics to elucidate the nature and/or causality of the AE or SAE as fully as possible. This may include additional laboratory tests or investigations, histopathological examinations, or consultation with other health care professionals.
- If a subject dies during participation in the study or during a recognised follow-up period, the investigator will provide Highlight Therapeutics with a copy of any postmortem findings including histopathology.
- New or updated information will be recorded in the originally completed eCRF.
- The investigator will submit any updated SAE data to Highlight Therapeutics, S.L within 24 hours of receipt of the information.

Reporting of SAEs

SAE Reporting to appropriate regulatory authorities

- Please follow the adverse event and serious adverse event guidelines.

Appendix 5 Excluded Medications/Therapy

Excluded medications/therapy is listed below. The use of an excluded medication/therapy is a protocol violation and must be recorded in the eCRF.

- Chemotherapy, definitive (curative) radiation, or biological cancer therapy within 4 weeks prior to the first dose of study treatment and during the study.
- Palliative radiotherapy (\leq 2 weeks of radiotherapy) within 1 week of start of study treatment. Palliative radiotherapy during the study may be allowed and should be discussed with the Sponsor. Lesions which receive palliative radiotherapy will be considered not evaluable as of the first day of the radiotherapy.
- Corticosteroids at physiologic doses exceeding 10 mg/day of prednisone or equivalent prior to start of treatment. Corticosteroid therapy is allowed during the study for the treatment of immune-related adverse events (See Section 1.1).
- Contraindications to tumour biopsy and injections of the hepatic metastasis(es), such as coagulopathy, therapeutic dose anticoagulant treatment and treatment with long-acting agents such as clopidogrel which cannot be safely stopped.
- Another investigational agent or device.

Appendix 6: Description of the iRECIST Process for Assessment of Disease Progression

Assessment at Screening and Prior to RECIST 1.1 Progression

Until radiographic disease progression based on RECIST 1.1, there is no distinct iRECIST assessment.

Assessment and Decision at RECIST 1.1 Progression

For subjects who show evidence of radiological PD by RECIST 1.1 as determined by the investigator, the investigator will decide whether to continue a subject on study treatment until repeat imaging is obtained (using iRECIST for subject management; see [Table 6](#)). This decision by the investigator should be based on the subject's overall clinical condition.

Clinical stability is defined as the following:

- Absence of symptoms and signs indicating clinically significant progression of disease
- No decline in ECOG performance status
- No requirements for intensified management, including increased analgesia or other palliative care. In case of need for palliative radiotherapy, possible treatment continuation should be discussed with Sponsor.

Any subject deemed **clinically unstable** should be discontinued from study treatment at site-assessed first radiologic evidence of PD and is not required to have repeat tumour imaging for confirmation of PD by iRECIST.

If the investigator decides to continue treatment, the subject may continue to receive study treatment and the tumour assessment should be repeated 4-6 weeks later to confirm PD by iRECIST, per investigator assessment.

Tumour flare may manifest as any factor causing radiographic progression per RECIST 1.1, including:

- Increase in the sum of diameters of target lesion(s) identified at baseline to $\geq 20\%$ and ≥ 5 mm from nadir
 - Note: the iRECIST publication uses the terminology “sum of measurements”, but “sum of diameters” will be used in this protocol, consistent with the original RECIST 1.1 terminology.
- Unequivocal progression of non-target lesion(s) identified at baseline
- Development of new lesion(s)

iRECIST defines new response categories, including iUPD (unconfirmed progressive disease) and iCPD (confirmed progressive disease). For purposes of iRECIST assessment, the first visit showing progression according to RECIST 1.1 will be assigned a visit (overall) response of iUPD, regardless of which factors caused the progression.

At this visit, target and non-target lesions identified at baseline by RECIST 1.1 will be assessed as usual.

New lesions will be classified as measurable or non-measurable, using the same size thresholds and rules as for baseline lesion assessment in RECIST 1.1. From measurable new lesions, up to 5 lesions total (up to 2 per organ), may be selected as new lesions – Target. The sum of diameters of these lesions will be calculated and kept distinct from the sum of diameters for target lesions at baseline. All other new lesions will be followed qualitatively as new lesions – nontarget.

Assessment at the Confirmatory Imaging

On the confirmatory imaging, the subject will be classified as progression confirmed (with an overall response of iCPD), or as showing persistent unconfirmed progression (with an overall response of iUPD), or as showing disease stability or response (iSD/iPR/iCR).

Confirmation of Progression

Progression is considered confirmed, and the overall response will be iCPD, if ANY of the following occurs:

- Any of the factors that were the basis for the initial iUPD show worsening
 - For target lesions, worsening is a further increase in the sum of diameters of ≥ 5 mm, compared to any prior iUPD time point
 - For non-target lesions, worsening is any significant growth in lesions overall, compared to a prior iUPD time point; this does not have to meet the “unequivocal” standard of RECIST 1.1
 - For new lesions, worsening is any of these:
 - An increase in the new lesion sum of diameters by ≥ 5 mm from a prior iUPD time point
 - Visible growth of new non-target lesions
 - The appearance of additional new lesions
- Any new factor appears that would have triggered PD by RECIST 1.1

Persistent iUPD

Progression is considered not confirmed, and the overall response remains iUPD, if:

- None of the progression-confirming factors identified above occurs AND
- The target lesion sum of diameters (initial target lesions) remains above the initial PD threshold (by RECIST 1.1)

Additional imaging for confirmation should be scheduled 4 to 8 weeks from the imaging on which iUPD is seen. This may correspond to the next visit in the original visit schedule. The assessment

of the subsequent confirmation imaging proceeds in an identical manner, with possible outcomes of iCPD, iUPD, and iSD/iPR/iCR.

Resolution of iUPD

Progression is considered not confirmed, and the overall response becomes iSD/iPR/iCR, if:

- None of the progression-confirming factors identified above occurs, AND
- The target lesion sum of diameters (initial target lesions) is not above the initial PD threshold.

The response is classified as iSD or iPR (depending on the sum of diameters of the target lesions), or iCR if all lesions resolve.

In this case, the initial iUPD is considered to be pseudo-progression, and the level of suspicion for progression is “reset”. This means that the next visit that shows radiographic progression, whenever it occurs, is again classified as iUPD by iRECIST, and the confirmation process is repeated before a response of iCPD can be assigned.

Management Following the Confirmatory Imaging

If repeat imaging does not confirm PD per iRECIST, as assessed by the investigator, and the subject continues to be clinically stable, study treatment may continue and follow the regular imaging schedule. If PD is confirmed, subjects will be discontinued from study treatment.

NOTE: If a subject has confirmed radiographic progression (iCPD) as defined above, but the subject is achieving a clinically meaningful benefit, an exception to continue study treatment may be considered following consultation with the Sponsor. In this case, if study treatment is continued, tumour imaging should continue to be performed following the scheduled intervals.

Detection of Progression at Visits After Pseudo-progression Resolves

After resolution of pseudo-progression (ie, achievement of iSD/iPR/iCR), iUPD is indicated by any of the following events:

- Target lesions
 - Sum of diameters reaches the PD threshold ($\geq 20\%$ and ≥ 5 mm increase from nadir) either for the first time, or after resolution of previous pseudo-progression. The nadir is always the smallest sum of diameters seen during the entire study, either before or after an instance of pseudo-progression.
- Non-target lesions
 - If non-target lesions have never shown unequivocal progression, their doing so for the first time results in iUPD.

- If non-target lesions have shown previous unequivocal progression, and this progression has not resolved, iUPD results from any significant further growth of non-target lesions, taken as a whole.
- New lesions
 - New lesions appear for the first time
 - Additional new lesions appear
 - Previously identified new target lesions show an increase of ≥ 5 mm in the new lesion sum of diameters, from the nadir value of that sum
 - Previously identified non-target lesions show any significant growth

If any of the events above occur, the overall response for that visit is iUPD, and the iUPD evaluation process (see Assessment at the Confirmatory Imaging above) is repeated. Progression must be confirmed before iCPD can occur.

The decision process is identical to the iUPD confirmation process for the initial PD, with 1 exception: if new lesions occurred at a prior instance of iUPD, and at the confirmatory imaging the burden of new lesions has increased from its smallest value (for new target lesions, the sum of diameters is ≥ 5 mm increased from its nadir), then iUPD cannot resolve to iSD or iPR. It will remain iUPD until either a decrease in the new lesion burden allows resolution to iSD or iPR, or until a confirmatory factor causes iCPD.

Additional details about iRECIST are provided in the iRECIST publication.

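### Appendix 6 lets iUPD resolve to iSD or iPR without requiring the new lesion or non-target progression that triggered it to have regressed, which can inflate iRECIST ORR and DCR

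*Combined protocol and SAP*

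**What the plan says.** Appendix 6 of the protocol sets the iRECIST rules. The first visit with RECIST 1.1 progression "will be assigned a visit (overall) response of iUPD, regardless of which factors caused the progression". A new lesion alone, or non-target progression alone, is therefore enough for iUPD.

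The confirmatory scan has three possible outcomes:

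- **iCPD:** a factor behind the iUPD worsens, or "Any new factor appears that would have triggered PD by RECIST 1.1". For measurable new lesions, worsening means "An increase in the new lesion sum of diameters by ≥ 5 mm from a prior iUPD time point".
- **Persistent iUPD:** two conditions must both hold. The first is "None of the progression-confirming factors identified above occurs AND"; the second is "The target lesion sum of diameters (initial target lesions) remains above the initial PD threshold (by RECIST 1.1".
- **Resolution:** no confirming factor, as above, and "The target lesion sum of diameters (initial target lesions) is not above the initial PD threshold".

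On resolution, "The response is classified as iSD or iPR (depending on the sum of diameters of the target lesions), or iCR if all lesions resolve". The text continues: "In this case, the initial iUPD is considered to be pseudo-progression", and the level of suspicion is reset.

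Section 8.1 takes iRECIST best response over all time points. Table 8 counts iPR in both iRECIST ORR and iRECIST DCR, and counts iSD of at least 12 weeks in iRECIST DCR. Both are secondary endpoints.

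**The concern.** The two categories that do not confirm progression are separated by the target sum, although the target sum may have had nothing to do with the iUPD. When the trigger lies outside the target lesions and simply persists, the scan is recorded as resolved pseudo-progression while the progression is still visible.

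The setting makes this pattern plausible. Section 8.1 requires the injected liver lesion, if measurable, to be a target lesion. A local injection effect could lower the target sum while disease appears elsewhere.

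The effect runs in one direction. A subject who would otherwise stay iUPD, and count as a non-responder without disease control, can move into iRECIST ORR or DCR. None moves the other way.

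**Working it through.** The plan gives no figure for this rule, so the first step is to apply the rule as written.

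**Step 1. Label at the first confirmatory scan.** Inputs are the three Appendix 6 outcomes above. In the new-lesion and non-target rows, the target sum is not above the PD threshold. 'Not worse' means that no confirming criterion is met. The last column applies the rule proposed under the fix.

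| Sole trigger of iUPD | State at repeat scan | Label now | Label under the fix |
|---|---|---|---|
| New lesion | Worse | iCPD | iCPD |
| New lesion | Present, unchanged | iSD/iPR | iUPD |
| New lesion | Smaller or gone | iSD/iPR | iSD/iPR |
| Non-target | Worse | iCPD | iCPD |
| Non-target | Present, unchanged | iSD/iPR | iUPD |
| Non-target | Smaller or gone | iSD/iPR | iSD/iPR |
| Target sum | Not worse, still above threshold | iUPD | iUPD |
| Target sum | Not worse, no longer above threshold | iSD/iPR | iSD/iPR |

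Only the two 'unchanged' rows differ. An unchanged lesion has not worsened and is not a new factor, so it cannot give iCPD. With the target sum at or below the threshold it cannot give persistent iUPD either. Resolution is the only category left.

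**Step 2. Does later text repair this?** The end of Appendix 6 blocks resolution on account of new lesions, but only in a later iUPD episode and only when new-lesion burden has risen from its smallest value. An unchanged lesion at the first episode is not covered. After the reset, a fresh iUPD needs growth, additional lesions or target progression, so an unchanged lesion does not bring iUPD back. The same subsection does treat a fall in new-lesion burden as what permits resolution, which is the condition missing earlier.

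**Step 3. When does an endpoint change?**

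- *ORR:* only if partial-response shrinkage is first documented at or after the iUPD scan. Appendix 6 has no separate iRECIST assessment before RECIST 1.1 progression, so an earlier response already counts.
- *DCR:* only if disease control was not already met before iUPD. An iPR then counts directly; an iSD needs at least 12 weeks. For example, a new lesion at Week 7 that is unchanged at Week 13 gives iSD 13 − 1 = 12 weeks after first dose. It would count if duration runs from first dose, which is an assumption. The counting sentence in Table 8 omits the 12-week condition that its own definition contains.

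**Step 4. Weight of one subject.** The formula is 1/N, with N the full planned cohort size (Section 9.1).

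- Cohort A: 1/26 = 3.8 percentage points.
- Cohort B: 1/43 = 2.3 percentage points.

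For illustration, with exact Clopper-Pearson 95% limits (an assumption, since Table 8 names no method):

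- Cohort A: 3/26 = 11.5% (2.4 to 30.2) becomes 2/26 = 7.7% (0.9 to 25.1).
- Cohort B: 9/43 = 20.9% (10.0 to 36.0) becomes 8/43 = 18.6% (8.4 to 33.4).

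**The case against.** **Other lesions are examined.** A reader might infer that the target sum alone decides resolution. The text does not support that: the first condition excludes any confirming factor, so worsening new or non-target lesions give iCPD. The gap is confined to lesions that have not met a worsening criterion and have not regressed.

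**Many such subjects are already counted, or never reach the rule.** Those with a response or long enough stable disease before iUPD add nothing. Clinically unstable subjects are not required to have a repeat scan. Both points stand, and they limit the number affected.

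**It may be a deliberate convention.** Appendix 6 itself foresees subjects whose non-target progression remains unresolved after iUPD has resolved, and it refers to the iRECIST publication for further detail. A reader might infer that the appendix departs from published iRECIST. The documents cannot show that, and no such finding is made here. Intent would not remove the one-directional effect on two named endpoints.

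**The discrepancy would be visible.** RECIST 1.1 ORR and DCR are reported alongside, and Section 9.3 provides individual listings. This stands and limits the seriousness, but a reader of the listings would have no rule for correcting the iRECIST rates.

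**The appendix also guides treatment.** Table 6 attaches different actions to repeat iUPD and to iSD or iPR, so a general rewording would reach beyond the analysis. This stands, and the fix is limited accordingly.

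**Conclusion.** The point holds for iUPD triggered solely by a new lesion or non-target progression that is present and unchanged at the repeat scan, with the target sum not above the PD threshold. Appendix 6 then yields iSD or iPR, and the subject can enter iRECIST ORR or DCR under the conditions in Step 3. The size is 3.8 points per subject in Cohort A and 2.3 in Cohort B, at full planned enrolment.

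Two stronger readings should be resisted. A reader might infer a total inflation of the iRECIST rates; the documents do not say how many subjects would show this pattern, so no total can be given. A reader might also infer that the main result is at risk. It is not: the primary ORR, DOR, PFS and the Simon response counts all use RECIST 1.1. The matter is worth correcting because it affects two secondary efficacy endpoints and the change is small.

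**What to change.** In the iBOR derivation used for iRECIST ORR and DCR (Table 8 and the SAP), state that, when no confirming factor occurs at a scan after iUPD:

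- the scan is iSD or iPR only if the initial target sum is not above the PD threshold **and** every new-lesion or non-target trigger of that iUPD has decreased or disappeared;
- otherwise the scan stays iUPD;
- iCR continues to require that all lesions resolve.

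The categories are mutually exclusive: a trigger that has shrunk but is still visible permits iSD or iPR, and one that has not shrunk keeps iUPD. This matches the wording on new-lesion burden at the end of Appendix 6. The SAP should also say how a decrease is judged, by the sum of diameters for measurable new lesions and qualitatively for the rest.

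The cost is a short addition to the derivation and its programming, and recording of the state of each trigger at repeat scans. iRECIST ORR and DCR may be slightly less favourable.

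For treatment decisions, the sponsor should reconcile the resolution and persistence rules of Appendix 6 with Table 6 and state which classification Table 6 uses. No treatment rule is proposed here.
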